Zogenix is developing a new formulation of fenfluramine hydrochloride, ZX008, for the adjunctive treatment of DS. Studies ZX008-1501 and 1502 are two randomized controlled trials of two fixed doses of ZX008 (Fenfluramine HCl) as an adjunctive therapy in children and young adults with DS. Study 1501 is conducted in North America (Canada and the USA), and 1502 is being conducted in Europe and Australia (Australia, Belgium, Denmark, France, Germany, Italy, Spain, Sweden, and the United Kingdom). The objective of each study is to demonstrate that ZX008 0.8 mg/kg/day is superior to placebo as adjunctive therapy in the treatment of DS in children and young adults based on change in the frequency of convulsive seizures between baseline and the combined Titration and Maintenance Periods (T+M). Study ZX008-1504 is a multicenter, 2-Cohort trial to first assess the pharmacokinetic and safety profile of a single dose of ZX008 (Fenfluramine Hydrochloride) oral solution when added to standard of care (Cohort 1), followed by a randomized, double-blind, placebo-controlled parallel group evaluation of the efficacy, safety, and tolerability of ZX008 as adjunctive antiepileptic therapy to stiripentol treatment in children and young adults with DS (Cohort 2).

The purpose of this Statistical Analysis Plan (SAP) is to outline the planned analyses and presentation of the clinical data from protocol ZX008-1503, dated 08 February 2018 (amendment 4.0), an international, multicenter, open-label, long-term safety study of ZX008 in pediatric and young adult subjects with DS who have successfully completed 14 weeks of treatment in core study ZX008-1501, ZX008-1502, and ZX008-1504 Cohort 2, or successfully completed core study ZX008-1504 Cohort 1, and are candidates for continuous treatment for an extended period of time. In addition, subjects who are >18 to ≤35 years of age at the time of screening, and who meet all other eligibility criteria may be eligible for participation after discussion with the Medical Monitor and sponsor about the potential risks and benefits for receiving ZX008. Participation for these subjects will be at the discretion of the sponsor.

Amendment 3 of this clinical trial extended the initial 12-month study period to 24 months, and Amendment 4 extended the duration to 36 months. Thus, with the implementation of Amendment 4, this clinical trial will consist of an up to 36-month Open-Label Extension (OLE) Treatment Period and a 2-week Post-Dosing

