6.1.7.2 Seizure Diaries

Seizures are recorded in the Daily Seizure Diary, while the End of Day Diary provides Yes/No confirmation that that seizures were experienced for a specific date, or that the date was seizure free.

- If no seizures are entered in the DSD and the EDD confirms seizure freedom, the number of seizures for that date is zero.
- If seizures are entered in the DSD and the EDD states seizures freedom, the seizures recorded for that date supersede the EDD stating seizure freedom.
- If no seizures are entered in the DSD and there is no response in the EDD, that day will be considered to have missing diary data.
- If no seizures are entered in the DSD and there is a Yes response in the EDD, that day will be considered to have missing diary data.

Handling of missing date information for AEs:

- The term *missing date* refers to a completely missing date or to an incomplete date/partial date where parts are not available, e.g. missing month/day/year.
- Missing start and end date will be imputed conservatively, i.e. missing values will be imputed in such a way that the duration of the AE is considered with the longest possible duration and such that, whenever the AE may potentially start after first IMP, the AE will be handled as a TEAE.
- The missing start date and end date of AE will be imputed for the purpose of calculating treatment emergent status and assigning events to treatment periods using definitions given in the following table.

Table 8 Data Conventions for Missing Adverse Event Start or Stop Dates

Start or End Date Missing	Data Convention
Partial /Missing Start date	
Missing day – If Adverse event day is missing but month and year are present then Impute the 1st of the month unless month is same as month of first dose of study drug then impute first dose date.
 
Missing day and month – If adverse event day and month are both missing but year is present then impute 1st January unless year is the same as first dose date then impute first dose date.
 
Completely missing – impute first dose date unless the end date suggests it could have started prior to this in which case impute the 1st January of the same year as the end date.
 
When imputing a start date, ensure that the new imputed date is sensible i.e. is prior to the end date of the AE.

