Partial /Missing End date	
If the AE is “ongoing”, do not impute an end date.
 
The following applies to a missing end date where the AE is not “ongoing”:
 
Missing day – If AE end day is missing but month and year are present then Impute the last day of the month unless month is same as month of last dose of study drug then impute last dose date.
 
Missing day and month – If AE has missing day and month but year is present then impute 31st December unless year is the same as the last dose date then impute last dose date.
 
Completely Missing – need to look at whether the AE is still ongoing before imputing a date and when it started in relation to study drug. If the ongoing flag is missing then assume that AE is still present (i.e. do not impute a date). If the AE has stopped and start date is prior to first dose date then impute the 1st dose date, if it started on or after first dose date then impute a date that is after the last dose date.

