Treatment-Emergent Adverse Events by MedDRA System Organ Class and Preferred Term
Safety Population (Japan)

Table 14.3.1.2.1.1
Treatment-Emergent Adverse Events during Open-label Treatment Periods by Age Group (<6 yrs, ≥6 yrs), MedDRA System Organ Class and Preferred Term
Safety Population

Programming note: Similar to Table SADS21 in ISS, but population is 1503 Safety, and only use AEs occurring during 1503. One column only, ALL subjects in ZX008 OL. Alternatively, this is just the above Table, 14.3.1.2.1, by Age Group.

Programming Note: Use the shell for 14.3.1.2.1.1 to produce same format for 14.3.1.2.1.4.

Table 14.3.1.2.1.4
Treatment-Emergent Adverse Events during Open-label Treatment Periods by Age Group (<6 yrs, ≥6 yrs), MedDRA System Organ Class and Preferred Term
Safety Population (Japan)

Table 14.3.1.2.1.2
Treatment-emergent Adverse Events with Decreased Appetite or Hypophagia during Open-Label Treatment Period
Safety Population

	Placebo (N = xxx)	ZX008 0.2 mg (N = XXX)	ZX008 0.5 mg (N = XXX)	ZX008 0.8 mg (N = XXX)	ZX008 OL (N = XXX)	De Novo Subjects (N = XXX)
Decreased Appetite	XX (XX.X%)	XX (XX.X%)	XX (XX.X%)	XX (XX.X%)	XX (XX.X%)	XX (XX.X%)
Had adverse event unresolved	XX (XX.X%)	XX (XX.X%)	XX (XX.X%)	XX (XX.X%)	XX (XX.X%)	XX (XX.X%)
Duration of event for subjects who had event resolved	XX (XX.X%)	XX (XX.X%)	XX (XX.X%)	XX (XX.X%)	XX (XX.X%)	XX (XX.X%)
n	XX	XX	XX	XX	XX	XX
Mean	XX.X	XX.X	XX.X	XX.X	XX.X	XX.X
SD	XX.XX	XX.XX	XX.XX	XX.XX	XX.XX	XX.XX
Median	XX	XX	XX	XX	XX	XX
Min, Max	XX	XX	XX	XX	XX	XX
Hypophagia	XX (XX.X%)	XX (XX.X%)	XX (XX.X%)	XX (XX.X%)	XX (XX.X%)	XX (XX.X%)
Had adverse event unresolved	XX (XX.X%)	XX (XX.X%)	XX (XX.X%)	XX (XX.X%)	XX (XX.X%)	XX (XX.X%)
Duration of event for subjects who had event resolved	XX (XX.X%)	XX (XX.X%)	XX (XX.X%)	XX (XX.X%)	XX (XX.X%)	XX (XX.X%)
n	XX	XX	XX	XX	XX	XX
Mean	XX.X	XX.X	XX.X	XX.X	XX.X	XX.X
SD	XX.XX	XX.XX	XX.XX	XX.XX	XX.XX	XX.XX
Median	XX	XX	XX	XX	XX	XX
Min, Max	XX	XX	XX	XX	XX	XX

TEAE = Treatment-Emergent Adverse Event.

Note: Events considered are all TEAEs occurring during OLE. Adverse events are classified as treatment-emergent if they started on or after the date of first dose of study treatment. Adverse events with partial or missing start dates are classified as treatment-emergent, unless the non-missing components of the start date confirm otherwise.

Programmin note: Please see annotations in ISS for SST16

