Programming notes: If subjects has multiple events with the same preferred term, count the worst case (if one event is unresolved, count the unresolved one).

Programming Note: Use the same shell for 14.3.1.2.1.5 (Japan).

Programming Note: Use the shell for Table 14.3.1.2.1) for the following Tables:

Table 14.3.1.2.2
Treatment-Emergent Adverse Events occurring in at least 5% of the subjects by MedDRA System Organ Class and PT
Safety Population

For the interim: Since we are only tabulating for “All subjects”,
Add the footnote: “Events listed are those for which the % of subjects having that AE is $\geq 5.0\%$ of subjects.”

Table 14.3.1.3
TEAEs leading to study discontinuation by MedDRA System Organ Class and Preferred Term
Safety Population

Table 14.3.1.3.1
TEAEs leading to study discontinuation by MedDRA System Organ Class and Preferred Term
Safety Population (Japan)

Table 14.3.1.4
Serious TEAEs by MedDRA System Organ Class and Preferred Term
Safety Population

Table 14.3.1.4.1
Serious TEAEs by MedDRA System Organ Class and Preferred Term
Safety Population (Japan)

Table 14.3.1.5.1
Related TEAEs MedDRA System Organ Class and Preferred Term
Safety Population

Table 14.3.1.5.2
Related TEAEs occurring in at least 5% of subjects by MedDRA System Organ Class and Preferred Term
Safety population

Table 14.3.1.5.3
Related TEAEs MedDRA System Organ Class and Preferred Term
Safety Population (Japan)

Table 14.3.1.5.4
Related TEAEs occurring in at least 5% of subjects by MedDRA System Organ Class and Preferred Term
Safety population (Japan)

TLF Shells

Zogenix International Limited
ZX008-1503

For the interim: Since we are only tabulating for "All subjects",
Add the footnote: "Events listed are those for which the % of subjects having that AE is $\geq 5.0\%$ of subjects."

PUBLIC COPY
This document cannot be used to support any marketing authorization application and any extensions or variations thereof.

Table 14.3.1.6
 TEAEs by Maximum Severity, MedDRA System Organ Class and Preferred Term
 Safety Population

MedDRA System Organ Class and Preferred Term	Maximum Severity	Gp1 (N=xx)	Gp 2 (N=xx)	Gp3 (N=xx)	Gp 4 (N=xx)	Gp5 (N=xx)	Gp 9 (N=xx)	De Novo Subjects (N=xx)
Subjects with any TEAE	Mild	XX (XX.X%)	XX (XX.X%)	XX (XX.X%)	XX (XX.X%)	XX (XX.X%)	XX (XX.X%)	XX (XX.X%)
	Moderate	XX (XX.X%)	XX (XX.X%)	XX (XX.X%)	XX (XX.X%)	XX (XX.X%)	XX (XX.X%)	XX (XX.X%)
	Severe	XX (XX.X%)	XX (XX.X%)	XX (XX.X%)	XX (XX.X%)	XX (XX.X%)	XX (XX.X%)	XX (XX.X%)

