TEAEs starting in the 3rd month of OLE by System Organ Class, Preferred Term and Prior Treatment in Feeder Study
Safety Population

Table 14.3.1.9.4.1
TEAEs starting in the 3rd month of OLE by System Organ Class, Preferred Term and Prior Treatment in Feeder Study
Safety Population (Japan)

Table 14.3.1.10.1
 Treatment-Emergent Adverse Events that Occurred in at least 5% of Subjects during Double-blind Treatment Period by MedDRA System Organ Class and Preferred Term
 with Mean Time to Onset (days) and Mean Duration (days)
 Safety Population

MedDRA System Organ Class and Preferred Term	Placebo (N=xx) n (%) / Mean Onset/ Mean Duration	ZX008 0.2 mg/kg/day (N=xx) n (%) / Mean Onset/ Mean Duration	ZX008 0.5 mg/kg/day (N=xx) n (%) / Mean Onset/ Mean Duration	ZX008 0.8 mg/kg/day (N=xx) n (%) / Mean Onset/ Mean Duration	Any DB ZX008 (N=xx) n (%) / Mean Onset/ Mean Duration
Subjects with any TEAE starting in the first month.	XX (XX.X%) / xx.x /xx.x	XX (XX.X%) / xx.x /xx.x	XX (XX.X%) / xx.x /xx.x	XX (XX.X%) / xx.x /xx.x	XX (XX.X%) / xx.x /xx.x
System Organ Class 1	XX (XX.X%) / xx.x /xx.x	XX (XX.X%) / xx.x /xx.x	XX (XX.X%) / xx.x /xx.x	XX (XX.X%) / xx.x /xx.x	XX (XX.X%) / xx.x /xx.x
Preferred Term 1	XX (XX.X%) / xx.x /xx.x	XX (XX.X%) / xx.x /xx.x	XX (XX.X%) / xx.x /xx.x	XX (XX.X%) / xx.x /xx.x	XX (XX.X%) / xx.x /xx.x
Preferred Term 2	XX (XX.X%) / xx.x /xx.x	XX (XX.X%) / xx.x /xx.x	XX (XX.X%) / xx.x /xx.x	XX (XX.X%) / xx.x /xx.x	XX (XX.X%) / xx.x /xx.x

TEAE = Treatment-Emergent Adverse Event.

TEAE = Treatment-Emergent Adverse Event.

Note: Percentages are calculated based on the number of subjects in each treatment group.

Note: Mean Onset and Mean Duration are measured in days. The onset day is the study day at the adverse event onset. The duration is the number of days from onset to resolution or from onset to last follow-up day if the event was ongoing.

Note: Adverse events are classified as treatment-emergent if they started on or after the date of first dose of study treatment. Adverse events with partial or missing start dates are classified as treatment-emergent, unless the non-missing components of the start date confirm otherwise.

Note: In subjects with more than one occurrence of the same event, the time to onset and duration is based on the earliest occurring event.

Note: Time to onset is the number of days since first treatment with either ZX008 or placebo. The duration of an event is limited to the period of the double-blind study.

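### Planned adverse-event durations either treat ongoing events as ended or leave them out, so they are biased downward, mainly at early data cuts and in the table limited to the double-blind period

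*SAP*

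**What the plan says.** Three rules in the SAP bear on adverse-event duration.

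- **Appetite table.** The shell of Table 14.3.1.2.1.2, also used for 14.3.1.2.1.5 (Japan), has for each term a row "Had adverse event unresolved" with number and percentage. Below it are n, mean, SD, median and range under "Duration of event for subjects who had event resolved". For subjects with several events of the same term, the programming note says to "count the worst case (if one event is unresolved, count the unresolved one".
- **Duration tables.** The notes to Tables 14.3.1.10.1 and 14.3.1.10.2 state: "The duration is the number of days from onset to resolution or from onset to last follow-up day if the event was ongoing". Each cell holds number (%), mean onset and mean duration; there is no count of ongoing events. For repeat events the earliest is used. Table 14.3.1.10.1 adds: "The duration of an event is limited to the period of the double-blind study". The Japan copies, 14.3.1.10.1.1 and 14.3.1.10.2.1, use the same shells.
- **Dates.** Table 8 in Section 6.1.7.2 says that for an ongoing event the programmer should "do not impute an end date".

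No censored or time-to-resolution method for adverse events appears anywhere in the SAP.

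**The concern.** An event still ongoing at last contact is right-censored: only a lower bound on its duration is known. Averaging that bound as a completed duration pulls the mean down. Summarising only the resolved events selects those short enough to finish within the remaining follow-up.

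The primary objective is long-term safety and tolerability, and Section 6.4.2 gives decreased appetite and hypophagia their own tabulation. A reader will take a printed mean or median duration as the answer to how long the event lasts. With short follow-up, that figure mostly reflects the data cut.

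The outputs concerned include such cuts. Appendix 1 marks Table 14.3.1.2.1.2 for the 120-day safety update. It marks 14.3.1.2.1.5, 14.3.1.10.1.1 and 14.3.1.10.2.1 for the Japan report, which is triggered when all Japanese subjects have reached at least Month 3 (Section 1).

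**Working it through.** The SAP states no figure for adverse-event duration, so there is none to reproduce. The check has two parts.

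**Direction.** Let T be the true duration and C the time from onset to the end of follow-up.

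- The 14.3.1.10 tables report E[min(T, C)]. This is below E[T] whenever some events are ongoing, with no further assumption.
- The appetite table reports the mean or median of T given T ≤ C. Its mean is below E[T] when T is independent of C.

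**Size (illustrative).** Assumed, not from the SAP: T exponential with median 120 days, so λ = ln 2/120 = 0.005776 and the mean is 1/λ = 173.1 days. Follow-up F is 90 days (minimum at the Japan cut), 365 days (an intermediate value, not an SAP cut-off) or 1095 days (Month 36 target in the visit windows). Onset is either uniform over follow-up, or early: exponential with mean 30 days, capped one day before the end of follow-up.

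For uniform onset the last-follow-up mean has a closed form. With x = λF, P(ongoing) = (1 − e^(−x))/x and E[min(T, C)] = (1/λ)(1 − P(ongoing)).

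- F = 90: x = 0.520, P = 0.780, mean = 173.1 × 0.220 = 38.1 days.
- F = 365: x = 2.108, P = 0.417, mean = 173.1 × 0.583 = 101.0 days.
- F = 1095: x = 6.325, P = 0.158, mean = 173.1 × 0.842 = 145.8 days.

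The other entries come from simulation of 2,000,000 events per row.

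| F (days) | Onset | Resolved | Resolved-only median (true 120) | Last-follow-up mean (true 173.1) |
|---|---|---|---|---|
| 90 | early | 29% | 30.0 (−75%) | 50.5 (−71%) |
| 90 | uniform | 22% | 23.4 (−81%) | 38.1 (−78%) |
| 365 | early | 85% | 96.4 (−20%) | 147.8 (−15%) |
| 365 | uniform | 58% | 66.5 (−45%) | 101.0 (−42%) |
| 1095 | early | 99.8% | 119.9 (0%) | 173.0 (0%) |
| 1095 | uniform | 84% | 100.4 (−16%) | 145.8 (−16%) |

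**Table 14.3.1.10.1.** Its window is the double-blind study whatever the date of the report. Subjects "successfully completed 14 weeks of treatment in core study" (Section 1), so F = 14 × 7 = 98 days. Under the same model the last-follow-up mean is 55.7 days (early onset, −68%) or 40.9 days (uniform onset, −76%), against 173.1.

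**Kaplan-Meier comparator.** In a separate run with uniform onset and follow-up to Day 1099, censoring ongoing events gave medians of 30, 90, 180 and 366 days for true medians of 30, 90, 180 and 365. With 90 or 98 days of follow-up and true medians of 180 days or more, it returned not reached. The planned summaries would instead print means of about 28 to 38 days (resolved only) or 40 to 64 days (last follow-up).

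**The case against.** The best defence concerns the appetite table. Its duration row is labelled as resolved-only, the unresolved count stands directly above it, and a subject with any unresolved event is classed as unresolved. A reader might infer that the plan conceals persistent events; it does not. Listing 16.2.7.1 also gives start, stop and outcome for each event. This stands, and is a reason to keep those rows and add to them. It does not help the 14.3.1.10 tables, which show no ongoing count.

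Other inferences the SAP does not support:

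- **That unresolved events are by definition the longest.** An event starting just before the cut is unresolved and may be short. The selection is only towards shorter events among those resolved.
- **That the double-blind limit in 14.3.1.10.1 is an error.** It is the table's stated scope. What is missing is treatment of events crossing that boundary as censored.
- **That the two table families contradict each other.** They cover different periods and select different events (worst case against earliest), so their durations would differ even under one censoring rule.
- **That the SAP breaks its own principle.** The aim that "missing values will be imputed in such a way that the duration of the AE is considered with the longest possible duration" concerns missing dates, not ongoing events.

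Two uncertainties remain. Worst case among several resolved events is undefined. If it means the longest, that alone raises the per-subject figure (65 against 43 days for two events with true mean 43). The appetite shell also defers to annotations in the integrated safety summary, which are not at hand.

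Finally, the study is descriptive, Section 6.4.1.2 plans no inferential comparison of adverse events, and duration appears only in the shells. That limits the severity of the point, but the printed figures would still be misread.

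**Conclusion.** The point holds in this form. Mean duration in Tables 14.3.1.10.1, 14.3.1.10.2 and their Japan copies is biased downward whenever events are ongoing, and nothing in those tables shows how many are. In Tables 14.3.1.2.1.2 and 14.3.1.2.1.5 the omission is visible, but the mean and median are still not estimates of event duration.

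The size is conditional on exponential durations, a true median of 120 days and the two onset patterns; other values would give other figures. The bias matters mainly at early cuts such as the Japan report and in the table confined to 14 weeks. In a final report with full 36-month follow-up it is negligible for short events that begin early, so a claim of large understatement throughout would go too far. Month 3 is also only the minimum follow-up at the Japan cut. The change should be made, but nothing in the study's main conclusions depends on it.

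**What to change.** - **Tables 14.3.1.2.1.2 and 14.3.1.2.1.5.** Keep the unresolved count and the labelled resolved-only row. Add the Kaplan-Meier median (25th, 75th percentile) time from onset to resolution, with unresolved events censored at last adverse-event follow-up or data cut.
- **Tables 14.3.1.10.1, 14.3.1.10.2, 14.3.1.10.1.1 and 14.3.1.10.2.1.** Replace the plain mean duration by the Kaplan-Meier median with ongoing events censored, and show the number ongoing. In 14.3.1.10.1 and its Japan copy, censor at the end of the double-blind period. Print not reached where it applies.

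The cost is shell wording and a standard PROC LIFETEST call, a procedure the shells already use for the response curves; no new data are needed. Reported durations will become longer, and sparse terms, especially in the Japan subset, will often show not reached. Kaplan-Meier assumes that censoring is independent of duration, which fails if subjects discontinue because of the event. A footnote should say so.
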